## 8. SAFETY ANALYSES

The safety analyses will be based on the Safety population, unless otherwise specified.

### 8.1. Adverse Events Analyses

Adverse events analyses including summaries of adverse events (AEs), Serious (SAEs) and other significant AEs will be based on GSK Core Data Standards. As this is a placebo only device study and no active drug is prescribed, summaries will be provided for all participants combined regardless of their randomised treatment sequence. The details of the planned displays are provided in [Appendix 10: List of Data Displays](#).

A summary of the following AEs and SAEs will be provided:

- Any AE (pre treatment (SAE only)-, on- treatment or post-treatment)
- Any on-treatment drug related AE

- Any AE (pre-treatment or on-treatment) leading to permanent discontinuation of study treatment or withdrawal from study
- Any non-fatal SAE
- Any fatal SAE
- Any on-treatment non-fatal drug related SAE
- Any on-treatment fatal drug related SAE

AE incidence will be summarised overall using the primary System Organ Class (SOC) and preferred term. All listings of AEs/SAEs will identify whether each adverse event occurred pre-treatment, on treatment or after treatment.

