10.4.2. Safety Analyses

All safety analyses will be performed on the Safety Population.

Adverse events (AEs) will be coded using the standard GSK dictionary, Medical Dictionary for Regulatory Activities (MedDRA), and grouped by body system. The number and percentage of participants experiencing at least one AE of any type, AEs within each body system and AEs within each preferred term will be presented for each treatment group. Separate summaries will be provided for all AEs, drug related AEs, fatal AEs, non-fatal SAEs, AESIs and AEs leading to withdrawal.

Deaths and SAEs, if applicable, will be documented in case narrative format.

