## 2. SUMMARY OF KEY PROTOCOL INFORMATION

### 2.1. Changes to the Protocol Defined Statistical Analysis Plan

There were no changes or deviations to the originally planned statistical analysis specified in the protocol amendment 1 [(Dated: 17/MAY/2017)].

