**10.4.3. Treatment Emergent Flag for Adverse Events**

Flag	Definition
Treatment Emergent	
 
• As this study only administers placebo in both treatment periods, all AEs will be combined regardless of which device was used in each cross-over period to give the overall AEs associated with placebo.
 
• If AE onset date is on or after Visit 1 start date & on or before Visit 3 stop date.
 
• Visit 1 Date ≤ AE Start Date ≤ Visit 3 Date + 1 days
 

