**10.10.6. Safety Tables**

No.	Population	IDSL / TST ID / Example Shell	Title	Programming Notes	Deliverable
Adverse Events					
3.01	ITT	IDSL_AE1	Summary of Adverse Events		SAC
3.02	ITT	IDSL_AE1	Summary of On-Treatment Adverse Events		SAC
3.03	ITT	IDSL_AE1	Summary of Post-Treatment Adverse Events		SAC
3.04	ITT	IDSL_AE1	Most Common Non-Serious Drug Related Adverse Events	> 3 %	SAC
3.05	ITT	IDSL_AE1	Summary of Serious Adverse Events		SAC
3.06	ITT	IDSL_AE1	Summary of Serious Drug Related Events		SAC
3.07	ITT	IDSL_AE1	Most Common Serious Drug Related Adverse Events	> 3 %	SAC
3.08	ITT	IDSL_AE1	Summary of Fatal Adverse Events		SAC
3.09	ITT	IDSL_AE1	Summary of Non-Fatal Serious Adverse Events		SAC
3.10	ITT	IDSL_AE1	On-treatment AEs leading to Discontinuation of Study Treatment or Withdrawal from the Study		SAC
3.11	ITT	SAFE_T01	Summary of On-Treatment Moderate/Severe COPD Exacerbations		SAC
3.12	ITT	SAFE_T01	Summary of Post-Treatment COPD Moderate/Severe Exacerbations		SAC
3.13	ITT	IDSL_AE1	Summary of Serious Adverse Events by System Organ Class and Preferred Term (Number of Subjects and Occurrences)		SAC

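### The SAP pools all adverse events although the protocol promises them by treatment group, and SAP 2.1 declares no change

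*SAP*

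**What the plan says.** Protocol 10.4.2, in the current amendment, fixes the AE presentation: participants with any AE, AEs within each body system, and "AEs within each preferred term will be presented for each treatment group". It then names the categories: "Separate summaries will be provided for all AEs, drug related AEs, fatal AEs, non-fatal SAEs, AESIs and AEs leading to withdrawal".

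The SAP takes another route. Citing the placebo-only design, SAP 8.1 states that "summaries will be provided for all participants combined regardless of their randomised treatment sequence" and that "AE incidence will be summarised overall using the primary System Organ Class (SOC) and preferred term". SAP 10.4.3 adds that "all AEs will be combined regardless of which device was used in each cross-over period". Its treatment-emergent interval spans both periods: "Visit 1 Date ≤ AE Start Date ≤ Visit 3 Date + 1 days". SAP 8.2 defines no adverse events of special interest (AESIs). SAP 10.10.6 lists 13 safety tables, for example "Summary of Fatal Adverse Events" (Table 3.08), and none carries a note asking for columns by device.

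SAP 2.1 nevertheless declares: "There were no changes or deviations to the originally planned statistical analysis specified in the protocol amendment 1".

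**The concern.** In a crossover, nearly everyone in a single pooled column has used both regimens. That column cannot say on which regimen an AE, or an AE leading to withdrawal, began. The protocol promised that information and the SAP removes it, while the section meant to record departures says there are none. Anyone checking the study report against the protocol would find a presentation missing and no declared reason where reasons are supposed to be declared.

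The placebo-only reason also leaves two differences between the regimens unaddressed. The Protocol synopsis gives one daily inhalation for ELLIPTA and three for DISKUS + HandiHaler. The treatment table in Protocol 7.1 lists magnesium stearate for ELLIPTA only, although Protocol 3.3 and 3.3.1 describe the excipients collectively. Protocol 3.3.1 names excipient hypersensitivity and bronchospasm after inhaling as the risks, and either could in principle depend on the regimen.

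**Working it through.** The plan states no figure to reproduce. The check is mainly a comparison of texts, with a little arithmetic for the fix.

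**1. Is the protocol wording current, and was the matter left to the SAP?** Protocol 10.4.2 is current text, and the superseded protocol reproduced in the amendment history has the same sentence. The protocol leaves the analysis of the other endpoints (10.4.1) and any other analysis (10.4.3) to the analysis plan. It does not leave AE presentation.

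**2. Can the term *treatment group* be read so that the conflict disappears?**

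| Reading | Source | SAP text that contradicts it |
|---|---|---|
| Device regimen | Protocol 10.2 | SAP 10.4.3 pools across devices |
| Four randomised groups, 54 each | Protocol 5.2 | SAP 8.1 pools across sequences |

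SAP 2.1 is wrong on either reading.

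**3. Which listed tables serve the categories that Protocol 10.4.2 names?**

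| Protocol category | SAP 10.10.6 |
|---|---|
| All AEs | 3.01, and 3.02 (on-treatment) |
| Drug-related AEs | No complete table; only 3.04 (non-serious, >3%), 3.06 (serious), 3.07 (serious, >3%) |
| Fatal AEs | 3.08 |
| Non-fatal SAEs | 3.09 |
| AESIs | None (SAP 8.2) |
| AEs leading to withdrawal | 3.10 |

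Five tables match a named category, three are subsets of one, and five serve none (3.03, 3.05, 3.11, 3.12, 3.13): 5 + 3 + 5 = 13. SAP 8.1 itself names an on-treatment drug-related summary that the display list does not deliver. With N = 240, 3% is 7.2, so >3% means at least 8 participants. A related non-serious AE in 7 or fewer would appear in no drug-related table.

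**4. Denominators for regimen columns.** Protocol 10.2 plans 240 randomised, hence 120 per device sequence, with 10% loss: 0.10 × 240 = 24.

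- All 24 lost in period 2: 240 exposed to each regimen.
- All lost in period 1, 12 per sequence: 120 + 108 = 228 each.
- All lost in period 1 from one sequence: 120 + 96 = 216 for its second regimen, 240 for the other.

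**5. Planned inhalations per 28 days.** ELLIPTA: 1 × 28 = 28. DISKUS + HandiHaler: (2 + 1) × 28 = 84.

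**6. What a pooled line leaves open.** The documents give no expected AE rate, so this is an assumed range, with 240 exposed to each regimen and nobody having the event on both. Pooled counts of 5, 12 or 24 of 240 are 2.1%, 5.0% or 10.0%. Each is compatible with a near-even split (3 v 2, 6 v 6, 12 v 12) and with all events on one regimen. For 12 events that is 2.5% v 2.5% or 5.0% v 0%. The same is true of any pooled crossover table, so it is not evidence about this trial.

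**The case against.** The strongest reply is that the pooling is open and reasoned. SAP 8.1 and 10.4.3 both state it, 8.1 gives the reason, Protocol 3.3.3 calls the risk minimal, and there is no safety hypothesis. Exclusion criterion 7 already removes people with known hypersensitivity to the excipients. On this view the only demonstrable fault is a missing entry in SAP 2.1, and regimen columns are a preference. Much of this stands. It rules out any suggestion of concealment and limits the severity. It does not make SAP 2.1 true, and it does not supply the counts that the protocol promised.

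A second reply is that regimen-at-onset columns are not strictly the protocol's presentation. Protocol 10.3 makes the Safety population identical to ITT, analysed by randomised sequence, and *treatment group* is used in two senses. This stands: the columns are one reading, they are by regimen used, and the SAP should say so.

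A third is that attribution is already possible by hand from treatment sequence (Listing 05), event dates, the withdrawal listings (02, 12, 13) and the SAE narratives. That is partly true, but it does not replace tabulated counts and percentages. The AE listing shells are not reproduced, so they may already show the regimen. No defect in the listings is claimed.

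**Conclusion.** The point holds and is minor. Protocol 10.4.2 and the SAP conflict on AE presentation, and SAP 2.1 is incorrect. The effect is confined to descriptive safety reporting; the primary conclusion, the power and the sample size are unaffected.

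The conclusion on SAP 2.1 rests on text alone and needs no assumption about AE rates. That the AE tables have a single column is inferred from SAP 8.1 and 10.4.3, because their standard shell (IDSL_AE1) is not reproduced. The reproduced exacerbation shell shows an overall column only.

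Three stronger readings are tempting and not supported:

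- **That pooling hides a real difference between regimens.** The documents give no AE rate and no indication that a difference is expected.
- **That most of the 13 tables breach the protocol.** All-SAE tables (3.05, 3.13) are not a category named in Protocol 10.4.2, and 3.04 and 3.07 are only >3% subsets. Adding columns to those would not restore the drug-related summary.
- **That Visit 2 onsets can simply be given to period 2.** Protocol 5.1 and 9.1.1 have the returned inhaler(s) assessed before the new one(s) on that day, so an event following the first demonstration could be misattributed.

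**What to change.** 1. **Tables.** Beside the overall column, add columns by regimen in use at AE onset (ELLIPTA; DISKUS + HandiHaler) in 3.01, 3.02, 3.08, 3.09 and 3.10. The denominator of each is the number of participants who used that regimen. Add one complete on-treatment drug-related AE table in the same layout. Keep pre- and post-treatment events in the overall column only. Footnote that a participant with the event on both regimens counts once in each column.
2. **Definition.** State that *treatment group* is read as device regimen, as in Protocol 10.2, and that these columns are by regimen used rather than by randomised sequence.
3. **Visit 2 day.** Assign an onset by whether it began before or after first use of the new inhaler(s). Where the timing is unknown, flag the event and keep it in the overall column only.
4. **SAP 2.1.** Declare any pooling that remains, with its reason, and that no AESI summary is produced. If the sponsor keeps full pooling, this entry alone is the minimum correction.

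**Cost.** SAP wording, two columns in five tables, and one new table. Onset and visit dates are already needed for the definitions in SAP 10.4. The documents do not show whether onset time is collected, so some Visit 2 events may stay unassigned, and recorded onsets may cluster on visit days. Counts per column will be small, and DISKUS cannot be separated from HandiHaler.

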## **8.2. Adverse Events of Special Interest Analyses**

There are no adverse events of special interest in this study as this is a placebo only device study.

### **8.2.1. Cardiovascular Events**

As for all non CV GSK studies, for subjects who report a cardiovascular event, individual patient profiles will be produced for one or more of the following categories:

- Myocardial infarction/unstable angina
- Congestive heart failure
- Arrhythmias
- Valvulopathy
- Pulmonary hypertension
- Cerebrovascular events/stroke and transient ischemic attack
- Peripheral arterial thrombosis
- Deep Venous Thrombosis
- Revascularization

### **8.2.2. Pregnancies**

Any pregnancies reported during the study will be summarised in case narratives. Any pregnancy complication or elective termination of a pregnancy for medical reasons will be recorded as an AE or SAE and included in summaries and listings of AEs/SAEs.

## **10. APPENDICES**

### **10.1. Appendix 1: Protocol Deviation Management and Definitions for Per Protocol Population**

The full list of protocol deviations collected on the eCRF is in the Protocol Deviation Management Plan (PDMP). Please refer to this document for current guidance.

There is no per protocol population in this study.

## 10.2. Appendix 2: Schedule of Activities

### 10.2.1. Protocol Defined Schedule of Events

Procedures	Visit 0 Screening (Can occur on same day as V1)	Visit 1 Randomization (Can occur on the same day as V0)	Visit 2 Assessment/ Cross-over	Visit 3 Last Visit/ End of Study
Study Day	1	1	28 (±2)	56 (±2)
Screening/safety assessments				
Written informed consent 	X			
Participant demography	X			
Medical/disease history including chronic obstructive pulmonary disease (COPD) history	X			
Therapy history	X			
Inclusion/exclusion criteria	X			
Concomitant medication	X		X	X
Physical examination 		X		
Vital signs 		X		
Adverse events (AEs)/ Serious adverse event (SAEs) 		X	X	X
Randomization 		X		
Study inhaler correct use and preference				
Participant reviews written instructions on the correct use of the newly dispensed inhaler(s)		X	X	
Assess participant's ability to correctly use the newly dispensed inhaler (following participant reading patient instruction leaflet (PIL) then demonstrating correct use) 		X	X	
Assess participant's ability to correctly use the returned inhaler(s) without instruction 			X	X
Assess compliance with the returned study inhaler(s) (based on the dose counter)			X	X
Preference Questionnaire				X

Procedures	Visit 0 Screening (Can occur on same day as V1)	Visit 1 Randomization (Can occur on the same day as V0)	Visit 2 Assessment/ Cross-over	Visit 3 Last Visit/ End of Study
Worksheets and medication				
Dispense study inhaler(s)		X	X	
Collect study inhaler(s)			X	X
Dispense Medical Problems/Medications Taken Worksheet 		X	X	
Collect and review Medical Problems/Medications Taken Worksheet 			X	X

1. Participants will be assigned a subject number at the time when the informed consent form (ICF) is signed. The ICF must be signed before any study procedures are conducted.
2. Results are recorded in the source documents only.
3. Refer to protocol Section 9.2.1.1 for AE/SAE data collection period.
4. Randomisation conducted if the Participant meets all study screening criteria.
5. A health care professional trained on the inhalers will conduct the assessments at Visits 1 and 2, following dispensing of the appropriate inhaler for the next dosing period.
6. A health care professional trained on the inhalers will conduct the assessments of the participant's ability to correctly use the returned inhaler (s) at Visits 2 and 3 following return of the inhaler (s) used for the previous dosing period. This should be completed at Early Withdrawal Visit if a participant has taken one or more doses of the inhaler at home.
7. Participants will record medical problems and medications taken on the Medical Problems/Medications Taken Worksheet between visits.
8. Safety assessments will be completed at the Early Withdrawal Visit: however, inhaler preference questionnaires will not be completed.

**10.3. Appendix 3: Assessment Windows****10.3.1. Definitions of Assessment Windows for Analyses**

Analysis Set / Domain	Parameter (if applicable)	Target	Analysis Window		Analysis Timepoint
			Beginning Timepoint	Ending Timepoint	
Efficacy	All	Day 28	Day 26	Day 30	Visit 2
		Day 56	Day 54	Day 58	Visit 3

As per the PDMP all assessments will be included in the analysis even if they are considered out of window.

## 10.4. Appendix 4: Study Phases and Treatment Emergent Adverse Events

### 10.4.1. Study Phases

Assessments and events will be classified according to the time of occurrence relative to Visit 1 (Study Day 1):

Study Phase	Definition
Pre-Treatment	Date < Study Treatment Start Date
On-Treatment	Study Treatment Start Date ≤ Date ≤ Study Treatment Stop Date +1
Post-Treatment	Date > Study Treatment Stop Date +1

### 10.4.2. Study Phases for Concomitant Medication

Treatment phases for summaries of COPD and non-COPD concomitant medications will be defined as follows:

Definition	Treatment Phase		
	Pre-Treatment	On-Treatment	Post-Treatment
Subject did not take study treatment (e.g, screening failures) and conmed stop date > date of Screening or variable that asks if conmed is on-going (refer hereafter as goingmed) is "yes"	Y		
(Conmed start date < treatment start date or variable that asks if medication taken prior to study is "yes" (refer hereafter as priormed)) and date of Screening < conmed stop date < treatment start date	Y		
(Conmed start date < treatment start date or priormed is yes) and treatment start date ≤ conmed stop date ≤ treatment stop date	Y	Y	
(Conmed start date < treatment start date or priormed is yes) and (conmed stop date > treatment stop date or goingmed is "yes")	Y	Y	Y
(Treatment start date ≤ conmed start date < treatment stop date and treatment start date ≤ conmed stop date ≤ treatment stop date) or (Treatment start date = conmed start date = conmed stop date = treatment stop date)		Y	
([Treatment start date ≤ conmed start date < treatment stop date] or [Treatment start date = conmed start date = treatment stop date]) and (conmed stop date > treatment stop date or		Y	Y

Definition	Treatment Phase		
	Pre-Treatment	On-Treatment	Post-Treatment
goingmed is Yes)			
Conmed start ≥ treatment stop date and treatment start date ≠ treatment stop date			Y

**NOTES:**

- A concomitant medication will be classed in every period of the study in which it was taken (e.g., run-in, on-treatment or post-treatment).
- See Section 10.7.2.1 for handling of partial dates.
- If the study treatment stop date is missing, it will be imputed as described in Section 10.6.1.
- Medications that stopped prior to Screening will not be assigned a treatment phase and will not be summarized.

**10.4.3. Treatment Emergent Flag for Adverse Events**

Flag	Definition
Treatment Emergent	
 
• As this study only administers placebo in both treatment periods, all AEs will be combined regardless of which device was used in each cross-over period to give the overall AEs associated with placebo.
 
• If AE onset date is on or after Visit 1 start date & on or before Visit 3 stop date.
 
• Visit 1 Date ≤ AE Start Date ≤ Visit 3 Date + 1 days
 

**NOTES:**

- If the study treatment stop date is missing, then the AE will be considered to be On-Treatment.

## 10.5. Appendix 5: Data Display Standards & Handling Conventions

### 10.5.1. Reporting Process

Software	

 
The currently supported versions of SAS software will be used.
 
The currently supported versions of TSCG software will be used.
 
	
Reporting Area	
HARP Server	: uk1salx00175
HARP Area	/arenv/arprod/gsk2834425/mid206901/final_01
Analysis Datasets	

 
Analysis datasets will be created according to Legacy GSK A&R dataset.
 
	
Generation of RTF Files	

 
RTF files will be generated for use in writing the CSR.
 
	

### 10.5.2. Reporting Standards

General	

 
The current GSK Integrated Data Standards Library (IDSL) will be applied for reporting, unless otherwise stated (IDSL Standards Location: https://spope.gsk.com/sites/IDSLLibrary/SitePages/Home.aspx):             
 
4.03 to 4.23: General Principles
 
5.01 to 5.08: Principles Related to Data Listings
 
6.01 to 6.11: Principles Related to Summary Tables
 
7.01 to 7.13: Principles Related to Graphics
 
 
 
Do not include subject level listings in the main body of the GSK Clinical Study Report. All subject level listings should be located in the modular appendices as ICH or non-ICH listings
 
	
Formats	

 
GSK IDSL Statistical Principles (5.03 & 6.06.3) for decimal places (DP's) will be adopted for reporting of data based on the raw data collected, unless otherwise stated.
 
Numeric data will be reported at the precision collected on the eCRF.
 
	
Unscheduled Visits	

 
Unscheduled visits will not be included in summary tables and/or figures.
 
All unscheduled visits will be included in listings.
 
	
Descriptive Summary Statistics	
Continuous Data	Refer to IDSL Statistical Principle 6.06.1
Categorical Data	N, n, frequency, %
Graphical Displays	

 
Refer to IDSL Statistical Principals 7.01 to 7.13.
 
	

## 10.6. Appendix 6: Derived and Transformed Data

### 10.6.1. Study Population

Treatment Compliance

 
Treatment compliance will be calculated for each inhaler separately based on the following formula:  <math display="block">\text{Treatment Compliance} = \frac{\text{Number of Actual Doses}}{(\text{Planned Treatment Duration in Days} * \text{Frequency})}</math> 
 
Frequency is 2 for BID and 1 for QD. Treatment compliance could be greater than 100% if there are events of overdose.
 

### 10.6.2. Efficacy

#### 10.6.2.1. Critical and Overall Errors

Critical and Overall errors

If a subject answered 'No' to any of the following it is considered a critical error for the ELLIPTA device:
 
 
Subject slides the cover completely down to expose the mouthpiece until a "click" is heard.
 
Subject does not shake the inhaler after the click is heard upon opening cover. (Note: a "Yes" response indicates that the subject did not shake the inhaler after the click is heard.)
 
Subject does not breathe out (exhale) into the mouthpiece. (Note: a "Yes" response indicates that the subject did not breathe into the mouthpiece.)
 
Subject places mouthpiece between lips, and closes lips firmly around it.
 
Subject takes one long steady deep breath in through their mouth.
 
 
If a subject answered 'No' to any of the following it is considered a critical error for the DISKUS device:
 
 
Subject opened cover
 
Subject slid the lever away from the mouthpiece as far as it would go until it clicked. Note: If the subject presses the lever more than once or slides the lever back to its starting position, this box should be checked No.
 
Subject did not tilt or shake the device after dose preparation Note: A Yes response means the subject did not tilt or shake the inhaler after preparing the dose
 
Subject did not exhale into the mouthpiece
 
Subject placed the mouthpiece between his/her lips
 
 
If a subject answered 'No' to any of the following it is considered a critical error for the HandiHaler device:
 
 
Subject opened the mouthpiece by pulling the mouthpiece ridge up and away from the base so the center chamber is showing
 
Subject appropriately only opened 1 capsule from the blister card
 
Subject placed the capsule in the center chamber of the inhaler
 
Subject closed the mouthpiece against the gray base, a click was heard, and the dust cap was left open
 

